13.8 Determination of sample size

The sample size estimate is based on the efficacy results observed in the adult RLS Phase 3 confirmatory study SP792, which was conducted in the USA. In this study, a range of rotigotine doses were compared to placebo.

The sample size calculation assumes that adolescent and adult patients will show a similar effect of rotigotine with respect to IRLS score and CGI (item 1) changes from Baseline in comparison to placebo, with a similar proportion of patients not included in the primary analysis.

In the adult study, the observed difference between the 3mg/24h rotigotine group and placebo in the change from Baseline to end of the 3-month Maintenance Period in IRLS sum score was 5.9. Already a difference between rotigotine and placebo of 4.0 points can be considered as clinically relevant. The common Standard Deviation (SD) estimate in the adult study was 7.9. For the CGI (Item 1), the difference between 3mg/24h rotigotine group and placebo was 0.6 with a SD of 1.2.

With these assumptions, a sample size of 45 evaluable patients in each group will provide a power of 93% for the IRLS endpoint, and a power of 87% for the CGI (Item 1) endpoint in the 3mg/24h dose. Assuming independence of the 2 endpoints will result in a power of 80% for the analysis of the co-primary variables. Since it is known that the 2 endpoints will have a relatively high correlation (approximately 0.7), the calculated 80% is a conservative estimator for the power.

Assuming similar effects for the 2mg/24h dose group, the conditional power for the 2mg/24h dose group is also 80% with an overall power for the study >60%. To obtain 135 evaluable subjects (ie, FAS), 138 patients have to be randomized (assuming approximately 2% of the randomized subjects cannot be utilized).

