13.3 Planned efficacy analyses

13.3.1 Analysis of the co-primary efficacy variables

Mean changes from Baseline to the end of the Maintenance Period in IRLS sum score and CGI (Item 1) in the 2 rotigotine arms (2mg/24h and 3mg/24h) will be compared with placebo to demonstrate superior efficacy of rotigotine.

The primary analysis of each co-primary variable will be based on a mixed model repeated measures (MMRM) analysis of covariance (ANCOVA) that includes terms for treatment group, visit, the respective Baseline score, and the interaction between treatment group and visit. The model will define patient as a random effect and utilize an unstructured covariance pattern. From this MMRM ANCOVA, treatment least-square (LS) means (with 95% confidence intervals [CI]) will be calculated and 1-sided 2 sample t-test will be performed (significance level 0.025) to test

the superiority of the rotigotine dose levels versus placebo, starting with 3mg/24h. The corresponding p-values will also be calculated.

The null hypotheses at each dose level are (H0): rotigotine is not superior compared to placebo. The alternative hypotheses are (H1): rotigotine is superior to placebo. Both co-primary endpoints must demonstrate significant results (at significance level 0.025) to demonstrate superiority of this dose level of rotigotine over placebo.

If the 3mg/24h dose is successful, the 2mg/24h dose level will be tested in the same way. Since both hypotheses have to be rejected in order to continue, multiplicity adjustment is not needed for the 2 hypotheses at each dose level. The multiplicity based on the two dose levels will be covered by applying the hierarchical approach (closed test procedure).

For subjects who prematurely withdraw for any reason before end of Maintenance, data collected during the Withdrawal Visit will be used to impute measurements at the next consecutive visit.

IRLS or CGI-1 measurements must be performed no longer than 1 day after the last patch removal to be utilized for analysis (valid measurements).

The above analyses will be performed on the FAS and the PPS. The primary analysis will be considered the analysis on the FAS.

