1 INTRODUCTION

This document contains details for the statistical analyses of study SP1006 which has been written in consideration of the International Council for Harmonization (ICH)/Food and Drug Administration (FDA) E9 Guidance documents (Phillips et al, 2003). The reader is referred to the study protocol and the electronic Case Report form (eCRF) for details of study conduct and data collection.

The Statistical Analysis Plan (SAP) describes the statistical principles that will be applied for the analyses as well as tables and listings that are foreseen for this study. Changes in the statistical methodology will result in an SAP amendment. Amendments to this document will be finalized prior to database lock.

This study was terminated early, and therefore the analysis described in this analysis plan is much more limited than that described in the protocol.

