2.5 Determination of sample size

The sample size estimate is based on the efficacy results observed in the adult RLS Phase 3 confirmatory trial SP792, which was conducted in the USA. In this study, a range of rotigotine doses were compared to placebo.

The sample size computation assumes that adolescent and adult patients will show a similar effect of rotigotine with respect to IRLS score and CGI (Item 1) changes from Baseline in comparison to placebo, with a similar proportion of patients not included in the primary analysis.

In the adult study, the observed difference between the 3mg/24h rotigotine group and placebo in the Change from Baseline to end of 3-month Maintenance Period in IRLS sum score was 5.9. A difference between rotigotine and placebo of 4.0 can be considered as clinically relevant. The common standard deviation (SD) estimate in the adult study was 7.9. For the CGI Item 1, the difference between 3mg/24h rotigotine group and placebo was 0.8 with a SD of 1.2.

With these assumptions, a total sample size of 45 evaluable patients in each group will provide a power of 93% for the IRLS endpoint, and a power of 87% for the CGI (Item 1) endpoint in the analysis of the 3mg/24h dose. Assuming independence of the 2 endpoints will result in a power of 80% for the analysis of the co-primary variables. Since it is known that the 2 endpoints will have a relatively high correlation (approximately 0.7), the calculated 80% is a conservative estimator for the power.

Assuming similar effects for the 2mg/24h dose group, the conditional power for the 2mg/24h dose group is also 80% with an overall power for the study $>60\%$. To obtain 135 evaluable patients (i.e., FAS), 138 patients must be randomized (assuming approximately 2% of the randomized patients cannot be utilized).

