8.1.2 Primary analysis of the primary efficacy variables

Observed results and changes from Baseline in IRLS sum score and CGI (Item 1) will be summarized by visit and by treatment group.

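### The protocol's CGI Item 1 difference of 0.6 gives 65% power at 45 per group, not the stated 87%; the SAP cites the same adult study with 0.8, which does reproduce it

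*Protocol*

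**What the plan says.** Protocol section 13.8 takes its effect sizes from the adult Phase 3 study SP792. For IRLS it uses a difference of 5.9 and an SD of 7.9. For the second co-primary it says: "For the CGI (Item 1), the difference between 3mg/24h rotigotine group and placebo was 0.6 with a SD of 1.2". On these inputs, with 45 evaluable subjects per group, it claims 93% power for IRLS and "a power of 87% for the CGI (Item 1) endpoint in the 3mg/24h dose". It then derives 80% for the co-primary pair if the endpoints are independent, calls this conservative because the endpoints correlate at about 0.7, and gives more than 60% for the study overall.

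SAP section 2.5 repeats this justification from the same adult study: same IRLS inputs, same CGI SD, same 45 per group, and the same 93%, 80% and >60%. Its CGI power is also unchanged: "a power of 87% for the CGI (Item 1) endpoint in the analysis of the 3mg/24h dose". The CGI difference is not the same: "the difference between 3mg/24h rotigotine group and placebo was 0.8 with a SD of 1.2".

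The test is set in Protocol section 13.3.1: "1-sided 2 sample t-test will be performed (significance level 0.025) to test" superiority over placebo. Both endpoints must be significant at that level, 3mg/24h is tested first, and 2mg/24h follows only if 3mg/24h succeeds.

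**The concern.** One observed result from one study cannot be both 0.6 and 0.8. SAP section 3.9, which lists changes to the protocol-defined analyses, does not mention the difference, and neither do the amendment logs of the two documents. Both statements are current text.

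CGI Item 1 is the weaker of two endpoints that must both succeed, so its power drives the co-primary power and, through the dose hierarchy, the overall power. If the design really rested on 0.6, every power figure below the IRLS line would be overstated and 45 per group would not deliver what the protocol claims. If it rested on 0.8, the design figures are sound and the protocol misreports an input. Either way, a reader of the protocol cannot reproduce the stated justification for 45 per group.

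**Working it through.** **Inputs.** One-sided alpha 0.025 (Protocol 13.3.1); n = 45 evaluable per group; IRLS 5.9, SD 7.9; CGI SD 1.2; CGI difference 0.6 (Protocol 13.8) or 0.8 (SAP 2.5); endpoint correlation about 0.7 (both documents).

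**Formula.** For a two-sample t-test, the noncentrality is δ = difference / (SD × √(2/n)), with df = 2n − 2 = 88 and critical value t = 1.987. Power is the probability that a noncentral t with df 88 and noncentrality δ exceeds 1.987.

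**Step 1: reproduce the IRLS figure.** δ = 5.9 / (7.9 × √(2/45)) = 5.9 / 1.665 = 3.543, giving 93.9% against 93% stated. The method matches the plan's own calculation without any covariate adjustment.

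**Step 2: CGI Item 1.** The standard error is 1.2 × √(2/45) = 0.253.

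- With 0.6: δ = 0.6 / 0.253 = 2.372, power **65.0%** (stated 87%).
- With 0.8: δ = 0.8 / 0.253 = 3.162, power **87.9%** (stated 87%).

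The difference that gives exactly 87% at SD 1.2 is 0.79.

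**Step 3: figures that depend on it.** The independence row multiplies the two endpoint powers. The correlation row uses a bivariate normal matched to those powers. The last row squares the independence figure, as the plan's own >60% does (0.80² = 0.64).

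| | Stated | With 0.6 | With 0.8 |
|---|---|---|---|
| CGI Item 1 | 87% | 65.0% | 87.9% |
| Co-primaries at 3mg/24h, independent | 80% | 0.939 × 0.650 = 61% | 0.939 × 0.879 = 82% |
| Co-primaries at 3mg/24h, correlation 0.7 | above 80% | 64% | 85% |
| Both doses | >60% | 0.610² = 37% | 0.825² = 68% |

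Squaring ignores the shared placebo arm. Allowing for it (correlation 0.5 between the two dose contrasts) raises the both-doses power at 0.6 to 44–49% for endpoint correlations of 0 to 0.7, still below 60%. A simulation of three arms of 45 agreed: 65.0% for CGI and 44–49% for both doses at 0.6.

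**Step 4: can 0.6 be reconciled with 87%?**

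- Rounding: inputs at the favourable edge (0.65, SD 1.15) give 75.5%.
- Alpha: one-sided 0.05 gives 76.1%. One-sided 0.10 gives 86.0%, but that contradicts section 13.3.1 and would put IRLS at 98.8%, not 93%.
- Baseline adjustment: 87% would need an SD of 0.91. No such reduction is described, and IRLS reproduces without one.
- Sample size: 0.6 with SD 1.2 needs 78 per group for 87%.

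**The case against.** The strongest reply is that little now depends on this. The SAP introduction says: "This study was terminated early, and therefore the analysis described in this analysis plan is much more limited than that described in the protocol". The interim analysis is cancelled (SAP 4.3), multiplicity is not applicable (SAP 4.5), and for the co-primaries "Observed results and changes from Baseline in IRLS sum score and CGI (Item 1) will be summarized by visit and by treatment group". The sample size can no longer be changed. That is correct, and it limits the point to the record of how the trial was sized.

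A second reply is that the design was very probably calculated with about 0.8, so the 0.6 figures should not be read as showing an underpowered trial. This also stands. All the stated powers fit 0.8 and, apart from IRLS, none fits 0.6.

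A third is that the recomputed powers ignore the futility rule in Protocol 13.7. Assuming 15 per arm at the interim and a normal approximation, that rule would lower co-primary power at 3mg/24h from 62–66% to 58–62% with 0.6, and from 84–86% to 78–81% with 0.8. However, the protocol's own 80% also leaves the rule out, so the comparison above is like for like. Restated figures should say that they exclude the interim.

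None of this explains how one study yields two differences, or how 0.6 yields 87%.

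**Conclusion.** The concern holds. As written, Protocol 13.8 gives a CGI input that yields 65.0% power, 22 percentage points below the 87% it states, and its 80% and >60% do not follow either. The SAP's 0.8 reproduces all three to within rounding or with a small margin, so 0.6 is probably a wrong digit. That is an inference from the arithmetic: the documents do not settle what the adult study observed, and the shortfall is real only if 0.6 is right.

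The figures assume a two-sample t-test at one-sided 0.025, 45 evaluable per group, no covariate adjustment and no interim stopping. The both-doses figures also assume the same effect at 2mg/24h, as the plan does. This should be corrected because it is the stated basis for the planned enrolment, but no conclusion from the remaining descriptive analyses depends on it.

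**What to change.** Check the CGI Item 1 difference and SD against the adult study report and state the same value in Protocol 13.8 and SAP 2.5.

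- **If 0.8 is right:** change 0.6 to 0.8 in Protocol 13.8. The stated power figures can stay.
- **If 0.6 is right:** correct SAP 2.5 and restate power in both documents, excluding the interim: about 65% for CGI Item 1; 61% (independence) to 64% (correlation 0.7) for the co-primaries at 3mg/24h; and about 37% (squared) or 44–49% (shared placebo arm) for both doses.

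The cost is most likely one digit in the protocol. In the other case it is a less favourable statement of planned power in both documents. No analysis in the current SAP changes either way.

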13.7 Planned interim analysis and data monitoring

An interim analysis for futility will be performed with approximately 33% of the planned number of evaluable subjects; recruitment will not be stopped for the interim analysis. The interim analysis will have three possible outcomes:

- Stop the study early for futility because rotigotine treatment at 3mg/24h meets the futility criteria (ie, no demonstrated benefit between active treatment and placebo to be expected at final analysis) regarding the primary objective of the study
- Stop recruitment into the rotigotine 2mg/24h arm for futility because rotigotine treatment at 2mg/24h seems futile regarding the primary objective of the study,
- Continue the study as planned.

No further changes to the protocol (eg, sample size adjustment) will be made as a result of the interim analysis.

The interim analysis will be conducted as soon as the end of the Maintenance/Premature Withdrawal Visit has been documented for 45 evaluable patients. The interim analysis will be performed on the data for the primary efficacy variable IRLS only and CGI Item 1 will not be considered. In case futility is achieved for the IRLS, this would also hold true for the CGI, since a lower effect size index for CGI is anticipated.

In the interim analysis, the change from Baseline to the end of the Maintenance Period in the score of the IRLS will be investigated. Estimates of treatment effect will be obtained separately for the two active treatment arms and Placebo from an MMRM ANCOVA model as described in [Section 13.3.1](#). Furthermore, the conditional power under the anticipated effect (anticipated effect and standard deviation will be utilized) according to Lan and Wittes (Siu and Lan, 2001) will be calculated for each of the treatment arms. The conditional power under the anticipated effect refers to the probability of concluding a positive result on the IRLS at the end of the study, assuming that the assumptions for the sample size estimation holds true.

The continuation criterion for each treatment arm is defined as applying both of the following conditions regarding the change from Baseline to the end of the Maintenance Period in the score of the IRLS:

- Treatment difference between the respective active group and placebo ≥ 2.0 points
- Conditional power under anticipated effect ≥ 60 %

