If at least 1 of these conditions fails, the continuation criterion is not met. [Table 13–1](#) shows the possible outcomes of the interim results and the corresponding decision rules.

Table 13–1: Decision rules at the interim analysis

Interim result	Decision
Failed continuation criterion for the 3mg/24h arm	Stop the study early
Met continuation criterion for the 3mg/24h arm Failed continuation criterion for the 2mg/24h arm	Remove the 2mg/24h arm and continue the study with the 3mg/24h arm and the placebo arm

Table 13–1: Decision rules at the interim analysis

Interim result	Decision
Met continuation criterion for the 3mg/24h arm Met continuation criterion for the 2mg/24harm	Continue the study as planned (with 3mg/24h and 2mg/24h arms plus placebo)

The interim analysis will be performed by an independent unblinded statistician not involved in any other study activity. Access to the interim results will be restricted to the statistician performing the analysis.

The study team will remain blinded and will be informed of the decision (stop the study early, stop a dose arm or continue the study as planned) without any supporting information. Details of the analysis will only be disclosed to the sponsor after study unblinding and will be provided in the clinical study report.

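### Protocol 13.8 states 93% IRLS and 80% co-primary power without saying that they leave out the 13.7 futility stop; with it, IRLS power is about 88% (86–92% by interim information)

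*Protocol*

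**What the plan says.** Protocol 13.8 takes its effect sizes from the adult Phase 3 study. It states that "a sample size of 45 evaluable patients in each group will provide a power of 93% for the IRLS endpoint", gives 87% for CGI Item 1, and obtains 80% for the co-primary pair by assuming independence. Because the endpoints are expected to correlate at about 0.7, it adds that "the calculated 80% is a conservative estimator for the power". It does not mention the interim analysis. SAP 2.5 repeats the same powers ("a total sample size of 45 evaluable patients in each group will provide a power of 93% for the IRLS endpoint").

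Protocol 13.7 sets a futility look on the IRLS once 45 evaluable patients have reached end of Maintenance or withdrawal, and "recruitment will not be stopped for the interim analysis". An arm continues only if two conditions hold. The first is "Treatment difference between the respective active group and placebo ≥ 2.0 points"; the second is conditional power of at least 60% under the planning effect. "If at least 1 of these conditions fails, the continuation criterion is not met", and Table 13-1 then stops the study if the failing arm is 3mg/24h. Nothing in 13.7 makes this advisory.

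Neither current document gives power with the stop, or the chance of stopping at any true effect.

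The documents also disagree on the CGI input. In the protocol the "difference between 3mg/24h rotigotine group and placebo was 0.6 with a SD of 1.2"; in the SAP the "difference between 3mg/24h rotigotine group and placebo was 0.8 with a SD of 1.2".

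**The concern.** A futility stop can only lower power, because some trials that would have succeeded are ended at the look. If the rule is followed as written, the design's chance of success is lower than the fixed-sample figure. A reader of 13.8 sees 93% and 80% as what the planned size delivers, with 80% described as conservative, and cannot tell how much of that the rule in the preceding section uses up. Nor can the reader see what the rule gains: how often it would end a study of an ineffective drug.

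**Working it through.** **Inputs.** One-sided alpha 0.025 (Protocol 13.3.1), so critical value 1.96. IRLS difference 5.9, SD 7.9, 45 per group, clinically relevant difference 4.0, endpoint correlation about 0.7 (Protocol 13.8). CGI SD 1.2 with difference 0.6 (Protocol 13.8) or 0.8 (SAP 2.5). Look at 45 evaluable in total, cut 2.0 points, conditional power 60% (Protocol 13.7). Assumption: equal split, so 15 per arm and information fraction t = 15/45 = 1/3.

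**1. Reproduce the stated powers (no interim).**
- IRLS: SE = 7.9·√(2/45) = 1.665; θ = 5.9/1.665 = 3.543; power = Φ(3.543 − 1.96) = 94.3%, or 93.9% by noncentral t with 88 df. Stated: 93%. At a true 4.0 the normal figure is 67.1%.
- CGI: SE = 1.2·√(2/45) = 0.253. A difference of 0.8 gives 88.5% (t: 87.9%), which matches the stated 87%. A difference of 0.6 gives 66.0% (t: 65.0%), which does not.
- Pair under independence: 0.93 × 0.87 = 80.9%; from the t-based values, 0.939 × 0.879 = 82.5%.

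So 93% is right as fixed-sample power. It cannot already include the stop (step 4).

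**2. Which condition decides.** Interim SE = 7.9·√(2/15) = 2.885. At an observed difference of 2.0, conditional power is Φ((2.0/2.885·√t + 3.543·(1 − t) − 1.96)/√(1 − t)) = Φ(0.98) = 83.7%. The 60% condition is met at any observed difference above about −0.97, so the 2.0-point cut decides. The 60% condition would bind only from about 28 per arm.

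**3. Chance of stopping the study.** P(stop) = Φ((2.0 − δ)/2.885).
- δ = 5.9: Φ(−1.352) = 8.8%
- δ = 4.0: Φ(−0.693) = 24.4%
- δ = 0: Φ(0.693) = 75.6%

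**4. IRLS power with the stop.** This is P(interim difference ≥ 2.0 and final Z > 1.96), bivariate normal with correlation √(1/3) = 0.577. It is 87.8% at 5.9, against 94.3% without the look, and 58.1% at 4.0, against 67.1%. Patient-level simulation with t-tests (200,000 trials) gives 87.5–87.6% at 5.9.

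**5. Sensitivity to interim information, and the co-primary pair.** True IRLS difference 5.9, CGI difference 0.8. The co-primary columns add the final CGI statistic as a third normal variable, with correlation ρ to the final IRLS statistic and ρ√t to the interim one.

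| Completers per arm at look | P(stop) | IRLS power | Co-primary, ρ = 0 | Co-primary, ρ = 0.7 |
|---|---|---|---|---|
| no look | – | 94.3% | 83.5% | 86.3% |
| 13 | 10.4% | 86.3% | 76.4% | 79.7% |
| 15 | 8.8% | 87.8% | 77.8% | 81.0% |
| 20 | 5.9% | 90.6% | 80.2% | 83.4% |
| 25 | 4.0% | 92.3% | 81.7% | 84.8% |

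Simulated t-tests run up to about 1 point lower: at 15 per arm the pair has 77.0% and 80.3%; at 25 per arm, 80.6% and 83.8%.

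**6. The stop against the CGI conflict.** With CGI 0.6 at 15 per arm, co-primary power falls from 62.2% to 57.9% (ρ = 0) and from 65.4% to 62.4% (ρ = 0.7). The stop therefore costs about 3 to 6 points. Moving the CGI difference from 0.8 to 0.6 costs about 21 (83.5 − 62.2).

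**The case against.** **No printed number is miscalculated.** The sentence in 13.8 is conditional on 45 evaluable per group, and neither document claims that 93% or 80% allows for the interim. This stands: a reader might infer an arithmetic error in the IRLS power, and step 1 shows there is none. What remains is that 13.8 presents these as the power the planned size provides, while the rule in the section before it takes part of that away.

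**Conservative is still true in its own sense.** In 13.8 the word compares independence with a correlation of 0.7. That ordering survives the stop in every row of the table. A reader might infer that 80% has simply ceased to be conservative. The documents do not support that without qualification. With CGI 0.8 and correlation 0.7, co-primary power with the stop is still roughly 80% or more, and the independence figure drops below 80% only when interim information is below about 20 completers per arm.

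**Fifteen per arm is an assumption.** Section 13.7 counts patients in total and keeps recruitment open. The interim MMRM can use earlier visits of patients still in Maintenance, while early withdrawals work the other way. This stands, and it is why the result is a range: at 25 per arm, IRLS power is only about 1 point below the printed 93%.

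**The record may be incomplete.** Protocol section 13 defers detail to the SAP, whose amendment log shows that section 2.4 once described actions after the interim. Stopping probabilities may have been given there. The point is limited to the current text.

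**Nothing now turns on it.** SAP 1 reports early termination, SAP 4.3 cancels the interim, and SAP 8.1.2 reduces the primary analysis to summaries. This settles the priority, but does not make the protocol's description of its design complete.

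**Conclusion.** The point holds as a gap in reporting. The 93% and 80% in Protocol 13.8 are fixed-sample figures, not labelled as such, and they leave out a study stop that 13.7 and Table 13-1 word as binding.

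At 15 per arm and a true 5.9, about 9% of trials stop and IRLS power is about 88%; for 13 to 25 completers per arm it is 86–92%. With CGI 0.8, co-primary power with the stop is about 77–78% (independence) or 80–81% (correlation 0.7) at 15 per arm, and about 81–82% or 84–85% at 25. The benefit also goes unreported: about 76% of trials end at the look if there is no effect.

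These figures rest on the planning effect and SD, a rule followed as written, and the assumed interim information. A baseline-adjusted MMRM could shrink the interim SE and with it the loss.

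A reader might infer that the futility rule is faulty or that the final results are affected. The documents support neither: a loss of this size can be a reasonable price for the stop, and the interim was never carried into the final analysis. The CGI conflict is a separate and larger error. Low priority: a change that could be made, not one that must be.

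**What to change.** In Protocol 13.8:

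1. Reconcile the CGI difference first (0.6 in the protocol, 0.8 in the SAP). The stated 87% reproduces only with 0.8; 0.6 gives 65%.
2. Label 93% and 80% as power without the interim, or restate them with the stop: IRLS about 88% at 15 per arm, range 86–92%, and co-primary power on the reconciled CGI value (at 15 per arm, about 77–81% at 0.8 or 57–62% at 0.6).
3. Add the probabilities of stopping the study at true differences of 5.9, 4.0 and 0 (about 9%, 24% and 76%), with the assumed number per arm at the look.
4. Limit the word conservative to the comparison of independence with correlation 0.7.

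In SAP 2.5, add one clause saying that the quoted powers are the planning-stage fixed-sample figures without the interim. SAP 4.3 cancels the look, so nothing more is needed there.

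No change to the rule in 13.7 is proposed. The cost is a few sentences and a slightly less favourable stated power, with no extra patients and no altered decision.

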Subjects will be administered study medication according to the dose titration schedule in [Section 7.2.1](#).

Subjects will be allowed to back-titrate 1 dose level during the Titration Period. Subjects are to complete the Titration Period at the back-titrated dose level and remain at this dose level for the duration of the Maintenance Period. If AEs occur during the Titration Period that are thought to

be the result of excessive dopaminergic stimulation (eg, intolerable nausea/vomiting), subjects should be back-titrated to their previous dose level and commence the Maintenance Period immediately. Subjects who do not tolerate the assigned dose in the first week (placebo or 1mg/24h) will be withdrawn from the study. If subjects withdraw due to lack of efficacy, they are eligible to roll over to the open-label study, RL0007, after the 3 weeks of the Titration Period are completed.

The Titration Period will be followed by a 12-week Maintenance Period. Subjects will remain at the assigned (or back-titrated) dose level throughout the Maintenance Period. At the end of the Maintenance Period, subjects will enter a Taper Period lasting up to a maximum of 4 days (de-escalation of study medication), followed by a 30-day Safety Follow-Up Period.

Visits will be scheduled every week during the Titration Period. During the Maintenance Period, visits will be scheduled every 4 weeks. There is a 4-day interval until the end of the Taper Period, followed by a 30-day interval (± 5 days) until the Safety Follow-Up Visit. Details are provided in the schedule of study assessments in [Section 5.2](#).

Plasma concentration of unconjugated rotigotine will be summarized by dose levels and visit. Plasma samples will be collected at Visit 6 and Visit 9.

An interim analysis for futility (for the primary outcome measures only), with the possibility of stopping the study early, stopping a dose arm, or continuing the study as planned, will be performed with approximately 33% of the planned number of evaluable subjects; recruitment will not be stopped for the interim analysis. The futility criteria are defined in [Section 13.7](#).

An overview of the study activities is given in [Table 5-1](#) and [Figure 5-1](#).

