13.1 Definition of analysis sets

The following analysis sets will be defined:

- Enrolled Set (ES): all subjects with a signed informed consent form and demographic data.
- Randomized Set (RS): all subjects from the ES who have been randomized.
- Safety Set (SS): all subjects from the RS who have at least 1 patch (rotigotine or placebo) applied. This population will be used for all safety analyses.

Full Analysis Set (FAS): all subjects from the SS who have a valid IRLS score and a valid CGI Item 1 score at Baseline and a valid post-Baseline IRLS score and a valid post-Baseline CGI Item 1 score. This population is the primary population for efficacy analysis.

- Per Protocol Set (PPS): all subjects from the FAS with no important protocol deviations (as specified in the data evaluation meeting) that could affect the co-primary variables and hence the efficacy evaluation. This population is the secondary population for efficacy analysis.

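### The 93%/87%/80% power figures assume full End-of-Maintenance data on 45 subjects per arm, but the 2% allowance covers only exclusion from the FAS, so missing Visit 9 scores lower power by an amount the plan never states

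*Protocol*

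**What the plan says.** **Power.** Protocol 13.8 takes its inputs from an adult study. The 3mg/24h-versus-placebo difference in change from Baseline to the end of the "Maintenance Period in IRLS sum score was 5.9", and "The common Standard Deviation (SD) estimate in the adult study was 7.9". It attaches 93% power for IRLS, 87% for CGI Item 1 and 80% for both together (under independence) to 45 evaluable subjects per group. It calls the 80% conservative because the endpoints correlate at about 0.7.

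**Allowance for loss.** The same section continues: "To obtain 135 evaluable subjects (ie, FAS), 138 patients have to be randomized (assuming approximately 2% of the randomized subjects cannot be utilized". SAP 2.5 agrees: "To obtain 135 evaluable patients (i.e., FAS), 138 patients must be randomized".

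**FAS.** Under Protocol 13.1, membership needs Baseline scores plus "a valid post-Baseline IRLS score and a valid post-Baseline CGI Item 1 score". No visit is named. SAP 3.5.4 is looser, since a valid pair on either endpoint is enough.

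**Withdrawals.** Under Protocol 13.3.1, "data collected during the Withdrawal Visit will be used to impute measurements at the next consecutive visit". SAP 4.2.1 imputes nothing at subsequent visits. Protocol 13.6 rules out replacing dropouts. Protocol 5.1 foresees exits: subjects who do not tolerate the first-week dose are withdrawn, and "If subjects withdraw due to lack of efficacy, they are eligible to roll over to the open-label study, RL0007" once Titration is complete.

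**Analysis.** Protocol 13.3.1 plans an MMRM over the post-Baseline visits (6, 7, 8 and 9), from which a "1-sided 2 sample t-test will be performed (significance level 0.025") compares each dose with placebo.

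**The concern.** The power formula treats all 45 subjects per arm as carrying full information on change to Visit 9. The recruitment formula counts subjects who have any post-Baseline score. These are different quantities, and the 2% bridges only from randomised to FAS.

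A subject assessed at Visit 6 who leaves before Visit 8 is in the FAS, but the Withdrawal Visit score fills Visit 7 or Visit 8 and Visit 9 stays empty. Nothing in either document covers that loss. The validity rule (measurement no later than 1 day after last patch removal) can remove further withdrawal scores.

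What is at stake is the reliability of the stated power. A reader of either document would take 80% as a floor, because both call it conservative, when it depends on a completion rate that is not given.

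**Working it through.** **Inputs.** IRLS 5.9, SD 7.9 (both documents). CGI Item 1 difference 0.8, SD 1.2 (SAP 2.5). One-sided alpha 0.025 (Protocol 13.3.1). 45 per arm. Endpoint correlation 0.7 (both documents). The share missing Visit 9 is in neither document, so 5%, 10%, 20% and 30% are assumptions.

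**Step 1: the plan's own figures.**
- Recruitment: 135/0.98 = 137.8, so 138. Reproduces.
- Power: noncentral t with 2n-2 df and noncentrality delta/(SD x sqrt(2/n)), n = 45.
- IRLS: 5.9/(7.9 x 0.2108) = 3.54, power 93.9% (stated 93%).
- CGI: 0.8/(1.2 x 0.2108) = 3.16, power 87.9% (stated 87%).
- Product: 0.939 x 0.879 = 82.5%. The rounded figures give 0.93 x 0.87 = 80.9% (stated 80%).
- Joint power at correlation 0.7, from a bivariate normal with these two margins: 85%.

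So the stated figures are what 45 complete End-of-Maintenance scores per arm deliver.

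With the CGI difference of 0.6 printed in Protocol 13.8, noncentrality is 2.37 and CGI power is 65% before any loss. Everything below therefore uses the SAP's 0.8.

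**Step 2: low end, Visit 9 scores only.** Put n = 45(1-d), where d is the share of FAS subjects without a Visit 9 score.

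| d | n per arm | IRLS | CGI | Product | Joint, corr. 0.7 |
|---|---|---|---|---|---|
| 0 | 45 | 93.9% | 87.9% | 82.5% | 85% |
| 5% | 42.75 | 92.7% | 86.1% | 79.8% | 83% |
| 10% | 40.5 | 91.3% | 84.2% | 76.9% | 81% |
| 20% | 36 | 87.8% | 79.7% | 69.9% | 76% |
| 30% | 31.5 | 83.1% | 74.0% | 61.5% | 69% |

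**Step 3: high end, crediting the MMRM.** Subjects with earlier visits still inform the Visit 9 contrast. Let R be the correlation matrix over Visits 6-9. Let subjects without Visit 9 be split evenly by last observed visit (6, 7 or 8). Sum the information 45 x w_k x inverse(R_k) over patterns, where w_k is the pattern's share and R_k the block of R for its observed visits. Then invert the sum: effective n is 1 divided by the Visit 9 diagonal element. R is an assumption. The most favourable case tried, equal correlation 0.8 between all visits, gives:

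| d | Effective n | Product | Joint, corr. 0.7 |
|---|---|---|---|
| 10% | 43.5 | 81% | 84% |
| 20% | 41.9 | 79% | 83% |
| 30% | 39.9 | 76% | 80% |

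Weaker correlation recovers less. At equal correlation 0.5, effective n is 41.9, 38.5 and 35.0.

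**Step 4: withdrawal is not the same as missing Visit 9.** A subject who leaves between Visits 8 and 9 has the Withdrawal Visit score used at Visit 9. If withdrawals were spread evenly over the 15 treatment weeks (an assumption), 4/15 = 27% would fall in that interval. A 20% withdrawal rate would then leave about 20% x 11/15 = 15% without a Visit 9 value.

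**The case against.** **The MMRM does not need 45 Visit 9 scores.** This stands. FAS members without Visit 9 contribute through earlier visits, and the next-visit rule rescues late leavers. A reader might infer that any ordinary dropout makes the stated power unattainable. The documents do not support that: they give no dropout rate, and at 5% missing the loss is negligible.

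**The 80% has margin.** This stands in part. At correlation 0.7 joint power starts at 85%. It stays above 80% at 10% missing, and at 20% under favourable MMRM recovery, but falls to 76% at 20% if only Visit 9 scores count. The 93% and 87% for the single endpoints have no such margin.

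**The adult figures may already reflect dropout.** Protocol 13.8 assumes a proportion outside the primary analysis similar to that in the adult study. If the 5.9 and 7.9 came from an analysis that gave every FAS subject a final value, FAS size would be the matching unit. The documents do not say how the adult analysis handled missing data, so this remains open. The assumption itself concerns exclusion from the analysis, not missing Visit 9 scores among those included.

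**There is no arithmetic error here.** This stands. 138 reproduces and, with the SAP's CGI difference, so do the power figures. The gap is an unstated assumption.

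**No test remains.** This stands. SAP 1, 3.9 and 8.1.2 report early termination and plan only by-visit summaries. A reader might fear that a non-significant result will be misread, but the current SAP produces no such result.

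**Conclusion.** The plan makes no allowance for missing End-of-Maintenance data within the FAS, and its power is below the stated basis by an amount that depends on an unstated rate. From Visit 9 scores only up to MMRM recovery at visit correlation 0.8, the independence product runs 77-81% at 10% missing, 70-79% at 20% and 62-76% at 30%, against 82.5% with none missing. Joint power at correlation 0.7 runs 81-84%, 76-83% and 69-80%, against 85%. This is negligible at 5%, small at 10% and material from about 20%.

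The result rests on the SAP's effects (5.9/7.9 and 0.8/1.2), 45 FAS subjects per arm, an assumed missing share, an assumed visit correlation, and adult inputs whose missing-data basis is not given. The Protocol's CGI difference of 0.6 is a separate and larger discrepancy: it undercuts the 87% and 80% even with complete data. The point bears on the design claim that both documents still carry, and on no planned analysis.

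**What to change.** In Protocol 13.8 and SAP 2.5:

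1. State that 93%, 87% and 80% assume full End-of-Maintenance information for 45 subjects per arm, and stop equating that with the FAS.
2. Keep the 2% as the allowance for exclusion from the FAS only.
3. Restate power for 138 randomised (46 per arm) over a stated range of missing Visit 9 scores, for example 10%, 20% and 30%, under the planned MMRM with its assumed visit correlation. Show joint power at the 0.7 endpoint correlation beside the independence product. Express the range as missing Visit 9, not as withdrawal.
4. Say that the restatement uses a CGI Item 1 difference of 0.8, and reconcile this with the 0.6 in Protocol 13.8.
5. Say how the adult analysis behind 5.9 and 7.9 treated subjects without a final score, or say that this is not known.

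The cost is wording and a short calculation. No patients, visits or analyses are added. The stated power becomes less favourable. With the study stopped, a note in the SAP and the study report would be enough.
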